8.3.2. Post-Study adverse events and serious adverse events

A post-study AE/SAE is defined as any event that occurs outside of the AE/SAE reporting period defined in [Table 15](#). Investigators are not obligated to actively seek AEs or SAEs in former study participants. However, if the investigator learns of any SAE at any time after a subject has been discharged from the study, and he/she considers the event reasonably related to the investigational vaccines, the investigator will promptly notify the Study Contact for Reporting SAEs.

8.3.3. Evaluation of adverse events and serious adverse events**8.3.3.1. Active questioning to detect adverse events and serious adverse events**

As a consistent method of collecting AEs, the subject should be asked a non-leading question such as: '*Have you felt different in any way since receiving the vaccine(s) or since the previous visit?*'

When an AE/SAE occurs, it is the responsibility of the investigator to review all documentation (e.g. hospital progress notes, laboratory and diagnostics reports) related to the event. The investigator will then record all relevant information regarding an AE/SAE in the eCRF. The investigator is not allowed to send photocopies of the subject's medical records to GSK instead of appropriately completing the eCRF. However, there may be instances when copies of medical records for certain cases are requested by GSK. In this instance, all subject identifiers will be blinded on the copies of the medical records prior to submission to GSK.

The investigator will attempt to establish a diagnosis pertaining to the event based on signs, symptoms, and/or other clinical information. In such cases, the diagnosis should be documented as the AE/SAE and not the individual signs/symptoms.

8.3.3.2. Assessment of adverse events**8.3.3.2.1. Assessment of intensity**

The intensity of the following solicited AEs will be assessed as described:

Table 16 Intensity scales for solicited adverse events

Adverse Event	Intensity grade	Parameter
Pain at injection site	0	None
	1	Mild: Any pain neither interfering with nor preventing normal every day activities.
	2	Moderate: Painful when limb is moved and interferes with every day activities.
	3	Severe: Significant pain at rest. Prevents normal every day activities.
Redness at injection site		Record greatest surface diameter in mm
Swelling at injection site		Record greatest surface diameter in mm
Fever(defined as temperature $\geq 38^{\circ}\text{C} / 100.4^{\circ}\text{F}$)*		Record temperature in $^{\circ}\text{C}/^{\circ}\text{F}$ Temperature will be analysed in 0.5°C increments from $\geq 38.0^{\circ}\text{C} / 100.4^{\circ}\text{F}$ Grade 3 fever is defined as $> 39.0^{\circ}\text{C} / 102.2^{\circ}\text{F}$
Headache	0	Normal
	1	Mild: Headache that is easily tolerated
	2	Moderate: Headache that interferes with normal activity
	3	Severe: Headache that prevents normal activity
Fatigue	0	Normal
	1	Mild: Fatigue that is easily tolerated
	2	Moderate: Fatigue that interferes with normal activity
	3	Severe: Fatigue that prevents normal activity
Gastrointestinal symptoms (nausea, vomiting, diarrhoea and/or abdominal pain)	0	Normal
	1	Mild: Gastrointestinal symptoms that are easily tolerated
	2	Moderate: Gastrointestinal symptoms that interfere with normal activity
	3	Severe: Gastrointestinal symptoms that prevent normal activity

* Fever is defined as temperature $\geq 38.0^{\circ}\text{C}/100.4^{\circ}\text{F}$ [Marcy, 2004] regardless of the location of measurement (oral is preferred)

The maximum intensity of local injection site (redness and swelling) will be scored at GSK Biologicals as follows:

0	:	≤ 20 mm
1	:	> 20 mm to ≤ 50 mm
2	:	> 50 mm to ≤ 100 mm
3	:	> 100 mm

The investigator will assess the maximum intensity that occurred over the duration of the event for all unsolicited AEs (including SAEs) recorded during the study. The assessment will be based on the investigator's clinical judgement.

The intensity should be assigned to one of the following categories:

- 1 (mild) = An AE which is easily tolerated by the subject, causing minimal discomfort and not interfering with everyday activities.
- 2 (moderate) = An AE which is sufficiently discomforting to interfere with normal everyday activities.
- 3 (severe) = An AE which prevents normal, everyday activities. Such an AE would, for example, prevent attendance at work/school and would necessitate the administration of corrective therapy.

An AE that is assessed as Grade 3 (severe) should not be confused with a SAE. Grade 3 is a category used for rating the intensity of an event; and both AEs and SAEs can be assessed as Grade 3. An event is defined as 'serious' when it meets one of the pre-defined outcomes as described in Section 8.1.2.

8.3.3.2.2. Assessment of causality

The investigator is obligated to assess the relationship between investigational vaccines and the occurrence of each AE/SAE. The investigator will use clinical judgement to determine the relationship. Alternative plausible causes, such as natural history of the underlying diseases, concomitant therapy, other risk factors, and the temporal relationship of the event to the investigational vaccines will be considered and investigated. The investigator will also consult the IB to determine his/her assessment.

There may be situations when a SAE has occurred and the investigator has minimal information to include in the initial report to GSK. However, it is very important that the investigator always makes an assessment of causality for every event prior to submission of the Expedited Adverse Events Report to GSK. The investigator may change his/her opinion of causality in light of follow-up information and update the SAE information accordingly. The causality assessment is one of the criteria used when determining regulatory reporting requirements.

In case of concomitant administration of multiple vaccines, it may not be possible to determine the causal relationship of general AEs to the individual vaccine administered. The investigator should, therefore, assess whether the AE could be causally related to vaccination rather than to the individual vaccines.

All solicited local (injection site) reactions will be considered causally related to vaccination. Causality of all other AEs should be assessed by the investigator using the following question: *Is there a reasonable possibility that the AE may have been caused by the investigational vaccine?*

- YES: There is a reasonable possibility that the study vaccination contributed to the AE.
- NO: There is no reasonable possibility that the AE is causally related to study vaccination. There are other, more likely causes and study vaccination is not suspected to have contributed to the AE.

If an event meets the criteria to be determined as 'serious' (see Section 8.1.2), additional examinations/tests will be performed by the investigator in order to determine ALL possible contributing factors for each SAE.

Possible contributing factors include:

- Medical history.
- Other medication.
- Protocol required procedure.
- Other procedure not required by the protocol.
- Lack of efficacy of the vaccine(s), if applicable.
- Erroneous administration.
- Other cause (specify).

8.3.3.3. Assessment of outcomes

The investigator will assess the outcome of all unsolicited AEs (including SAEs) recorded during the study as:

- Recovered/resolved.
- Recovering/resolving.
- Not recovered/not resolved.
- Recovered with sequelae/resolved with sequelae.
- Fatal (SAEs only).

8.3.3.4. Medically attended visits

For each solicited and unsolicited symptom the subject experiences, the subject will be asked if she received medical attention defined as hospitalisation, or an otherwise unscheduled visit to or from medical personnel for any reason, including emergency room visits. This information will be recorded in the eCRF.

8.4. Reporting of serious adverse events, pregnancies and other events

8.4.1. Prompt reporting of serious adverse events, pregnancies and other events to GSK

SAEs that occur in the time period defined in Section 8.3 will be reported promptly to GSK within the timeframes described in [Table 17](#), once the investigator determines that the event meets the protocol definition of a SAE.

Pregnancies that occur in the time period defined in Section 8.3 will be reported promptly to GSK within the timeframes described in Table 17, once the investigator becomes aware of the pregnancy.

Table 17 Timeframes for submitting serious adverse event and pregnancy to GSK

Type of Event	Initial Reports		Follow-up of Relevant Information on a Previous Report	
	Timeframe	Documents	Timeframe	Documents
SAEs	24 hours*‡	Electronic SAE report	24 hours*	Electronic SAE report
Pregnancies	2 weeks*	Electronic pregnancy report	2 weeks*	Electronic pregnancy report

*Timeframe allowed after receipt or awareness of the information.

‡The investigator will be required to confirm review of the SAE causality by ticking the 'reviewed' box in the electronic Expedited Adverse Events Report within 72 hours of submission of the SAE.

8.4.3. Completion and transmission of SAE reports to GSK

Once an investigator becomes aware that a SAE has occurred in a study subject, the investigator (or designate) must complete the information in the electronic Expedited Adverse Events Report WITHIN 24 HOURS. The report will always be completed as thoroughly as possible with all available details of the event. Even if the investigator does not have all information regarding a SAE, the report should still be completed within 24 hours. Once additional relevant information is received, the report should be updated WITHIN 24 HOURS.

The investigator will always provide an assessment of causality at the time of the initial report. The investigator will be required to confirm the review of the SAE causality by ticking the 'reviewed' box in the electronic Expedited Adverse Events Report within 72 hours of submission of the SAE.

8.4.3.1. Back-up system in case the electronic reporting system does not work

If the electronic reporting system does not work, the investigator (or designate) must complete, then date and sign a paper Expedited Adverse Event Report and fax it to the Study Contact for Reporting SAEs (refer to the [Sponsor Information](#)) or to GSK Clinical Safety and Pharmacovigilance department within 24 hours.

This back-up system should only be used if the electronic reporting system is not working and NOT if the system is slow. As soon as the electronic reporting system is working again, the investigator (or designate) must complete the electronic Expedited Adverse Events Report within 24 hours. The final valid information for regulatory reporting will be the information reported through the electronic SAE reporting system.

8.4.4. Completion and transmission of pregnancy reports to GSK

Once the investigator becomes aware that a subject is pregnant, the investigator (or designate) must complete the required information onto the electronic pregnancy report **WITHIN 2 WEEKS**.

Note: Conventionally, the estimated gestational age (EGA) of a pregnancy is dated from the first day of the last menstrual period (LMP) of the cycle in which a woman conceives. If the LMP is uncertain or unknown, dating of EGA and the estimated date of delivery should be estimated by ultrasound examination and recorded in the pregnancy report.

8.4.5. Updating of SAE and pregnancy information after removal of write access to the subject's eCRF

When additional SAE or pregnancy information is received after removal of the write access to the subject's eCRF, new or updated information should be recorded on the appropriate paper report, with all changes signed and dated by the investigator. The updated report should be faxed to the Study Contact for Reporting SAEs (refer to the [Sponsor Information](#)) or to GSK Clinical Safety and Pharmacovigilance department within the designated reporting time frames specified in [Table 17](#).

8.4.6. Regulatory reporting requirements for serious adverse events

The investigator will promptly report all SAEs to GSK in accordance with the procedures detailed in Section [8.4.1](#). GSK has a legal responsibility to promptly notify, as appropriate, both the local regulatory authority and other regulatory agencies about the safety of a product under clinical investigation. Prompt notification of SAEs by the investigator to the Study Contact for Reporting SAEs is essential so that legal obligations and ethical responsibilities towards the safety of other subjects are met.

Investigator safety reports are prepared according to the current GSK policy and are forwarded to investigators as necessary. An investigator safety report is prepared for (a) SAE(s) that is/are both attributable to the study vaccine and unexpected. The purpose of the report is to fulfil specific regulatory and GCP requirements, regarding the product under investigation.

8.5. Follow-up of adverse events, serious adverse events, and pregnancies

8.5.1. Follow-up during the study

After the initial AE/SAE report, the investigator is required to proactively follow each subject and provide additional relevant information on the subject's condition to GSK (within 24 hours for SAEs; refer to [Table 17](#)).

All AEs/SAEs documented at a previous visit and designated as either on-going, not recovered/not resolved or recovering/resolving will be reviewed at subsequent visits until the end of the study.

8.5.2. Follow-up after the subject is discharged from the study

The investigator will follow subjects with SAEs, or subjects withdrawn from the study as a result of an AE, until the event has resolved, subsided, stabilised, disappeared, or until the event is otherwise explained, or the subject is lost to follow-up.

If the investigator receives additional relevant information on a previously reported SAE, he/she will provide this information to GSK using a paper/ electronic Expedited Adverse Events Report and/or pregnancy report as applicable.

GSK may request that the investigator performs or arranges the conduct of additional clinical examinations/tests and/or evaluations to elucidate as fully as possible the nature and/or causality of the AE or SAE. The investigator is obliged to assist. If a subject dies during participation in the study or during a recognised follow-up period, GSK will be provided with any available post-mortem findings, including histopathology.

8.5.3. Follow-up of pregnancies

Pregnant subjects will be followed to determine the outcome of the pregnancy. At the end of the pregnancy, whether full-term or premature, information on the status of the mother and child will be forwarded to GSK using the electronic pregnancy report and the Expedited Adverse Events Report if applicable. Generally, the follow-up period does not need to be longer than six to eight weeks after the estimated date of delivery.

Regardless of the reporting period for SAEs for this study, if the pregnancy outcome is a SAE, it should always be reported as a SAE.

8.6. Treatment of adverse events

Treatment of any AE is at the sole discretion of the investigator and according to current good medical practice. Any medication administered for the treatment of an AE should be recorded in the subject's eCRF (refer to [Section 6.6](#))

8.7. Unblinding

GSK's policy (which incorporates ICH E2A guidance, EU Clinical Trial Directive and US Federal Regulations) is to unblind the report of any SAE which is unexpected and attributable/suspected to be attributable to the investigational vaccines, prior to regulatory reporting. The GSK's Central Safety Physician is responsible for unblinding the treatment assignment in accordance with the specified timeframes for expedited reporting of SAEs (refer to Section 8.4.1).

8.8. Emergency unblinding

Unblinding of a subject's individual treatment code should occur only in the case of a medical emergency, or in the event of a serious medical condition, when knowledge of the treatment is essential for the clinical management or welfare of the subject, as judged by the investigator.

The emergency unblinding process consists of the automated system SBIR that allows the investigator to have unrestricted, immediate and direct access to the subject's individual study treatment.

The investigator has the option of contacting a GSK On-call Central Safety Physician (or Backup) if he/she needs medical advice or needs the support of GSK to perform the unblinding (i.e. he/she cannot access SBIR).

Any emergency unblinding must be fully documented by using the Emergency Unblinding Documentation Form, which must be appropriately completed by the investigator and sent within 24 hours to GSK.

GSK Biologicals' Contact information for Emergency Unblinding 24/24 hour and 7/7 day availability	
GSK Biologicals' Central Safety Physician:	
Outside US:	
PPD	(GSK Biologicals Central Safety Physician on-call)
For US Only:	
PPD	(GSK Biologicals Central Safety Physician on-call)
GSK Biologicals' Central Safety Physician Back-up:	
Outside US:	
PPD	
For US Only:	
PPD	
Emergency Unblinding Documentation Form transmission:	
Outside US	
Fax: PPD	or PPD
For US Only:	
Fax: PPD	

8.9. Subject card

Study subjects must be provided with the address and telephone number of the main contact for information about the clinical study. The investigator (or designate) must therefore provide a “subject card” to each subject.

In an emergency situation this card serves to inform the responsible attending physician that the subject is in a clinical study and that relevant information may be obtained by contacting the investigator.

Subjects must be instructed to keep subject cards in their possession at all times during the study duration.

8.10. Holding rules and safety monitoring

8.10.1. Safety review team (SRT)

The SRT includes as core members the GSK’s Central Safety Physician, Central Safety Scientist, the Clinical and Epidemiology Project Lead (CEPL), Epidemiologist, Clinical Regulatory Affairs representative and the Biostatistician of the project. The SRT is responsible for on-going safety monitoring of the entire project and will meet on a regular basis. In order to keep all people involved in the conduct, cleaning and final analysis of the study blinded, the SRT will monitor safety in a **blinded** manner.

In addition to the existing SRT, unblinded safety evaluations will be performed by an iSRC at regular intervals and *ad hoc* as needed. The SRT will inform the iSRC about any potential safety concern relevant to the study and vice versa.

8.10.2. Internal Safety Review Committee (iSRC) Evaluation

As this will be the first time that the RSV maternal vaccine will be administered in humans, the study will enrol subjects in two steps with randomisation to all dose levels from the start (see also [Figure 1](#)). Safety monitoring will be performed by an iSRC, authorised by the GSK’s Vaccines Safety Monitoring Board (V SMB), and holding rules have been established to ensure the safety of the subjects in the study.

The iSRC will include the following GSK personnel: a Safety Physician (Vaccines Clinical Safety and Pharmacovigilance representative), a Clinician (CEPL or CRDL), and a Statistician, all external to the study/project and with no conflicts of interest in the outcome of the study. The GSK Safety Physician will act as the Chair of the iSRC. Additionally, the iSRC will have (a) *ad hoc*, non-voting member(s): (an) independent statistician(s) in charge of providing unblinded data to the iSRC.

This study has 3 planned iSRC reviews.

Only if no safety signal is observed during each of the 2 (Day 8 and Day 31) planned safety evaluations after the first 12% of subjects have been enrolled (Step 1) [See [Figure 1](#) and [Figure 2](#)], the screening and enrolment/vaccination of the remaining subjects (Step 2) can start.

Another iSRC review is planned to review the safety data up to at least Day 91 and immunogenicity data up to at least Day 31 for all subjects (Step 1 and Step 2) enrolled in the study.

In addition to the above planned iSRC evaluations, *ad hoc* iSRC reviews can be organized, as deemed necessary at any time during the study.

During the planned (and any *ad-hoc*, if applicable) iSRC safety evaluations, the iSRC will review all available safety data in an **unblinded** manner, while taking into account any other findings that could have an impact on the safety of the subjects, and will determine whether there is a safety signal or not.

Favourable outcome of the safety reviews will be documented and provided in writing to the RSV study team and investigator(s).

If a safety signal is observed during the planned safety evaluations or during *ad hoc* reviews, the iSRC Chair is responsible for urgent communication and escalation of the concern to the GSK's Chief Medical Officer (CMO), who may choose to involve the VSMB or VSMB sub-team, and will communicate the outcome to the study team. The CMO will then decide during an *ad hoc* meeting whether to suspend, modify or continue the conduct of the study.

Already vaccinated subjects will continue with all planned visits, including the capture of all safety data. However, further enrolment/vaccination cannot proceed until CMO (with or without the involvement of VSMB) review and corresponding outcome is available.

The decision of the GSK's iSRC will be documented and provided in writing to the Primary Contact for the study (study CRDL) who will ensure further communication of the outcome to investigator(s). Ethics Committees and Competent Authorities will also be notified, as applicable.

Details about the working procedures of the iSRC will be documented in an iSRC Charter.

8.10.3. Holding rules

The safety holding rules 1a through 1d, as defined in [Table 18](#), will be applied throughout the enrollment period of the study. In addition, the safety holding rules 2a through 2c will be applied for the iSRC reviews.

Table 18 Study holding rules

Holding Rule	Event	Number of Subjects per group/ % of subjects per group
1a	Death or any life-threatening SAE	≥ 1
1b	Any non-life threatening SAE that cannot reasonably be attributed to a cause other than vaccination	≥ 1
1c	Any withdrawal from the study (by investigator or subject request) following a Grade 3 AE that cannot reasonably be attributed to a cause other than vaccination	≥ 1
1d	Any local or general solicited AE leading to hospitalization , or fever $> 40^{\circ}\text{C}$ (104°F) that cannot reasonably be attributed to a cause other than vaccination, or necrosis at the injection site, within the 7-day (day 1-7) post-vaccination period	≥ 1
2a	Any Grade 3 solicited local AE lasting 48h or more in an investigational group, within the 7-day (day 1-7) post-vaccination period	$\geq 3 \text{ AND } \geq 20\%$
2b	Any Grade 3 solicited general AE lasting 48h or more in an investigational group, that cannot reasonably be attributed to a cause other than vaccination, within the 7-day (day 1-7) post-vaccination period	$\geq 3 \text{ AND } \geq 20\%$
2c	Any Grade 3 unsolicited AE in an investigational group, that cannot reasonably be attributed to a cause other than vaccination, within the 7-day (day 1-7) post-vaccination period OR Any Grade 3 abnormality in pre-specified hematological or biochemical laboratory parameters in an investigational group, that cannot reasonably be attributed to a cause other than vaccination, at day 8 post-vaccination ¹	$\geq 3 \text{ AND } \geq 20\%$

¹ Grading of laboratory parameters will be based on the FDA Guidance for Industry [APPENDIX C] "Toxicity Grading Scale for Healthy Adults and Adolescent Volunteers Enrolled in Preventive Vaccine Clinical Trials". Those laboratory parameters not included in the FDA Toxicity Grading Scale will not be graded.

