As this will be the first time that the RSV maternal vaccine will be administered in humans, the study will enrol subjects in two steps (Step 1 will enroll 60 subjects in the United States [US] only and Step 2 will enroll 440 subjects across multiple countries). Subjects will be randomised to all dose levels from the start. Both blinded and unblinded safety monitoring will be performed, as described below.

The Safety Review Team (SRT) will review blinded data on a regular basis throughout the study, and an internal Safety Review Committee (iSRC) will review unblinded data at specific study timepoints. (Refer to section[s] 8.10.1 and 8.10.2 for more details on the safety monitoring for this study).

During Step 1, until the first 30 subjects have been vaccinated, vaccination will be limited to 10 subjects/ per day across all sites. These subjects will be vaccinated sequentially and at least 60 minutes apart.

Subsequent vaccinations will continue without limitation to the number of subjects vaccinated per day or time lag between vaccination of consecutive subjects.

Screening and enrolment of Step 2 subjects will only be initiated if the iSRC review of Day 31 data results in a recommendation to proceed with Step 2.

Number of subjects Approximately 500 healthy women will be enrolled (~125/group).

Endpoint(s) **Primary**

- Occurrence of any adverse events (AEs) from vaccination during a 30-day follow-up period, for all subjects in all groups:
 - Occurrence of each solicited local and general symptom during a 7-day follow-up period.
 - Occurrence of any unsolicited AE during a 30-day follow-up period.
 - Occurrence of Serious AEs during a 30-day follow-up period.
 - Occurrence of any haematological (Leukocytes, Neutrophils, Lymphocytes, Eosinophils, Haemoglobin, Platelets) and biochemical (alanine aminotransferase [ALT], aspartate aminotransferase [AST], creatinine, blood urea nitrogen [BUN]) laboratory abnormalities at Day 8 and Day 31.

Secondary

- Occurrence of SAEs from vaccination up to Day 91 and up to Day 181 for all subjects, in all groups.
- Humoral immune response to the investigational vaccine at Day 8, Day 31, Day 61 and Day 91 for all subjects in each investigational RSV vaccine group
 - RSV-A neutralising antibody (Nab) titres;
 - RSVPreF3 immunoglobulin G (IgG) antibody concentrations

Tertiary

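### No planned iSRC review falls during Step 2 vaccination, so holding rules 2a-2c reach Step 2 data in time to act only if an ad hoc review is called

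*Protocol*

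**What the plan says.** Protocol 8.10.3 gives the two sets of holding rules different coverage. Rules 1a-1d "will be applied throughout the enrollment period of the study". For the group-level rules it says: "In addition, the safety holding rules 2a through 2c will be applied for the iSRC reviews". Table 18 sets the threshold for 2a-2c at 3 or more subjects and at least 20% of an investigational group. These rules use events in the first 7 days and laboratory values at Day 8.

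Protocol 8.10.2 states: "This study has 3 planned iSRC reviews". The first two use Step 1 data and gate Step 2: "Only if no safety signal is observed during each of the 2 (Day 8 and Day 31) planned safety evaluations" may the remaining women be screened and vaccinated. The Synopsis repeats the gate: "Screening and enrolment of Step 2 subjects will only be initiated if the iSRC review of Day 31 data results in a recommendation" to go ahead. The third is described thus: "Another iSRC review is planned to review the safety data up to at least Day 91", together with immunogenicity data, for all subjects of both steps. Section 10.11.1 also counts three planned evaluations. Section 8.10.2 allows ad hoc reviews whenever they are thought necessary.

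Protocol 8.10.1 says that "unblinded safety evaluations will be performed by an iSRC at regular intervals", and adds ad hoc evaluations as needed. The same section has the Safety Review Team (SRT) work on blinded data and pass any potential concern to the iSRC.

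On size, the Synopsis says: "Step 1 will enroll 60 subjects in the United States [US] only and Step 2 will enroll 440 subjects across multiple countries". After the first 30 women there is no limit on vaccinations per day or on the spacing between them.

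**The concern.** A holding rule is useful only if it is evaluated while there is still vaccination to hold. Rules 2a-2c are the only ones that compare the frequency of Grade 3 events within a dose group with a threshold, and they need unblinded counts. The plan schedules two such counts on the 15 women per group of Step 1, and none on Step 2 data until everyone has been vaccinated.

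This is a first-in-human vaccine, and Protocol 1.6.1 names the holding rules among its safeguards. A dose group with a rate of severe reactions at or above the plan's own 20% line can pass Step 1 by chance. About 110 more women would then receive that dose with no scheduled check of these rules.

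**Working it through.** **Timing, from the documents**

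| Planned review | Data | Step 2 vaccination at that point |
|---|---|---|
| 1 | Step 1, Day 8 | not started |
| 2 | Step 1, Day 31 | not started; waits for this review |
| 3 | all subjects, safety to at least Day 91 | finished |

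Protocol Table 5 allows Visit 5 at 86 to 100 days after the injection. At the third review the last vaccination therefore lies at least 86 days back. The data that rules 2a-2c read are complete at Day 8, about 91 - 8 = 83 days before the Day 91 visit. The Day 31 review of Step 1 adds no new women to these rules, so Step 1 amounts to one look at 15 per group.

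**Sizes.** Step 1: 60/4 = 15 per group. Step 2: 440/4 = 110 per group, or 3 x 110 = 330 on active vaccine. Step 2 share: 440/500 = 88%.

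**Reproducing Protocol 8.10.4 (15 per group).** At n = 15, 3/15 = 20%, so both parts of the rule 2 threshold coincide. With true rate p:

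- Rule 1 not met: (1-p)^15. At 5%: 0.95^15 = 0.463 (stated: more than 40%). Rule 1 met at 20%: 1 - 0.8^15 = 0.965 (stated: more than 90%).
- Rule 2 not met: sum over x = 0, 1, 2 of C(15,x) p^x (1-p)^(15-x). At 10%: 0.206 + 0.343 + 0.267 = 0.816 (stated: more than 80%). Rule 2 met at 30%: 1 - 0.127 = 0.873 (stated: more than 80%).

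All four statements reproduce.

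**Chance of passing Step 1.** The true rates here are assumptions. The one-group figures are for one rule. The last column assumes that all three dose groups share the rate and are independent.

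| True rate | One group does not meet the rule | No dose group meets it |
|---|---|---|
| 20% | 0.035 + 0.132 + 0.231 = 0.398 | 0.398^3 = 0.063 |
| 25% | 0.236 | 0.236^3 = 0.013 |
| 30% | 0.127 | 0.127^3 = 0.002 |

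**What blinded data show.** A 20% rate confined to one of four equal groups, with none elsewhere, appears as 20%/4 = 5% in pooled data.

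**What an evaluation during Step 2 could add.** The sizes below are assumed for illustration and are not proposals. Counts are cumulative, and the existing threshold is kept.

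| Women per group | 20% of group | Met at 25%, given Step 1 passed | Met at 30%, given Step 1 passed | Met at 10%, unconditional |
|---|---|---|---|---|
| 40 | 8 | 55% | 76% | 4.2% |
| 70 | 14 | 71% | 92% | 0.9% |

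**The case against.** Several points on the other side stand.

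- A reader might infer that rules 2a-2c cannot hold vaccination for any of the 440 Step 2 women, that they act on the 60 Step 1 women only, or that 88% of enrolment is beyond their reach. The documents do not support this. A rule met in Step 1 can block all of Step 2. Section 8.10.3 does not restrict the rules to planned reviews, ad hoc reviews are unblinded, and a signal at one stops further vaccination until the sponsor's chief medical officer has ruled.
- Rules 1a-1d cover Step 2 at a threshold of one subject, and include deaths, life-threatening events and serious events with no reasonable cause other than vaccination.
- The sentence in 8.10.1 on intervals also mentions ad hoc evaluations, so three planned reviews plus ad hoc ones is a possible reading of it.
- A rule with a 20% cut-off will often be missed at a true rate of exactly 20%. The plan discloses its design points (below 10% and above 30%), and these are correct. If all dose groups shared the rate, Step 1 would rarely clear all of them.
- Figure 1 is not shown. The iSRC charter and the separate SAP for the iSRC are not among the documents. Ad hoc triggers may be set out there.

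These points narrow the concern but do not remove it. An ad hoc review must be prompted, and the SRT that monitors routinely cannot see whether a dose group has reached 20%. A reaction confined to one dose is where pooled data are weakest. The 20% condition also adds nothing at 15 or fewer per group, where 3 events are already at least 20%. It matters only in larger groups, yet the plan schedules no evaluation of larger groups while vaccination is open.

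**Conclusion.** The point holds in this form: no planned iSRC review lies between the first and last Step 2 vaccination, so rules 2a-2c would be applied to Step 2 data in time to hold vaccination only through a discretionary ad hoc review with no trigger stated in the protocol. This fits poorly with the regular intervals of 8.10.1.

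The size depends on the assumed true rate. One dose group fails to meet a given rule 2 in Step 1 with probability 40% at 20%, 24% at 25% and 13% at 30%. About 110 further women in that group are then vaccinated before the next planned look. If all three dose groups shared the rate, the chance that none meets the rule is 6%, 1% and 0.2%. The figures assume exactly 15 per group and independent subjects. The protocol gives no enrolment rate for Step 2, so the time available for a review is unknown. The conclusion is limited to what the protocol and SAP show, and the charter or Figure 1 could change it.

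**What to change.** Reconcile Protocol 8.10.1, 8.10.2 and 8.10.3 so that the existing rules 2a-2c have a stated iSRC evaluation on Step 2 data while vaccination is still open. The timing is for the sponsor and the iSRC to set, and the rules and thresholds stay as they are. If the charter or the SAP for the iSRC already provides for this, a cross-reference in 8.10.3 is enough. Section 8.10.4 should then give operating characteristics for that evaluation as well, since it now covers only 15 per group.

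The cost is one more data cut by the independent statistician, one more meeting of the existing committee, and matching wording in the protocol and charter. An extra look also brings some chance of a hold at a low true rate. At a 10% rate this is about 4% per rule and group with 40 women per group, and about 1% with 70, both sizes being assumed.
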